Severe adverse events: pelvic infection (endometritis, cervicitis or pelvic inflammatory disease) as diagnosed by cervical culture and physical exam, spontaneous miscarriage (pregnancy loss prior to 20 weeks gestation) or increased contamination rates in the lab which is routinely monitored for by our embryologists.

Non-severe adverse events include adverse effects of antibiotic administration including yeast vaginitis, abdominal pain, diarrhea, nausea and vomiting.

5.d Classification of Events

Reportable severe events include development of pelvic infection following embryo transfer, a significant increase in spontaneous miscarriage rates or a note in increased contamination rates in the lab. Risks of pelvic infection in this low risk population following embryo transfer approaches zero and we do not anticipate this occurring. We anticipate miscarriage rates to be equivalent or improved in the non-prophylaxis group but will be closely tracked for any increase in incidence. The lab uses gentamicin routinely in embryo culture media to decrease contamination rates and will continue to be closely monitored as is standard for quality control measures in our lab for any increase in contamination rates.

Reportable non-severe adverse events include yeast vaginitis, nausea and vomiting or other adverse reactions from antibiotic prophylaxis which the patients will report to their nurses.

5.e Data Collection Procedures for Adverse Events

In addition to principle investigator review of adverse events, a data and safety monitoring board (DSMB) will be established. This will include [name], [name], [name] and [name] and [name], MSCI. The designated group will meet once enrollment reaches 50% and then every 6 months thereafter. Adverse events will be noted in the patients chart and in the redcap database for complete capture and tracking. Data will be analyzed if a noted increase in severe adverse events is noted or otherwise once enrollment reaches 50% and then every 6 months thereafter when the DSMB meets.

5.f Reporting Procedures

Patients will be instructed to report any adverse symptoms to their respective nurse or doctor. These events will be immediately reported to the PI or research project coordinator.

5.g Adverse Event Reporting Period

Until study completion.

-

F Statistical Plan

F1 Sample Size Determination and Power

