Given the conflicting evidence toward benefit of routine antibiotic prophylaxis and IVF outcomes, a non-inferiority approach was selected to test our hypothesis that no prophylaxis is not inferior to routine antibiotic administration. A total sample size of 356 patients (178 per arm) was determined based on an average baseline clinical pregnancy rate of 41% within our practice in this population with a non-inferiority margin of 15%, 80% power, and using a one sided $\alpha=0.025$ while estimating a 5% drop out rate. Our practice completed approximately 500 fresh IVF cycles in 2016. Our exclusion criteria are broad and we do not anticipate patient recruitment to be difficult. We believe 356 patients is feasible and estimate a 14 month timeline to complete recruitment if we enroll 7 patients at minimum per week.

F2 Interim Monitoring and Early Stopping

Interim analysis will be performed according to the Haybittle-Peto approach at 50% enrollment and 75% enrollment. This study will be considered safe to continue if there is an absence in trend toward severe adverse maternal, pregnancy or laboratory outcomes in either group. The DSMB will also assess recruitment progress and will review for futility of the trial in the context of lack of adequate recruitment. Data will be formally analyzed at 50% enrollment and then every 6 months thereafter to assess for early termination of the study.

F3 Analysis Plan

See Table 1 for timetable of patient enrollment and analysis. Our practice is required to track patient demographic data and cycle outcome measures to report to the Society for Assisted Reproductive Technology. Data are recorded and tracked through Research Electronic Data Capture (REDCap). Data from enrolled patients will be exported and tracked in a separate secure REDCap dataset from our existing dataset. All of our outcome measures are routinely tracked, and no additional data query will be required to address potential confounders as listed in Table 2.

F4 Statistical Methods

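### Severity is assigned by event type, not seriousness: every antibiotic reaction is non-severe by definition, so even a serious one cannot fire the off-schedule analysis in E5 5.e

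*Combined protocol and SAP*

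**What the plan says.** E5 5.c gives the severe class as three items. The first two are "Severe adverse events: pelvic infection (endometritis, cervicitis or pelvic inflammatory disease) as diagnosed by cervical culture and physical exam, spontaneous miscarriage" (loss before 20 weeks); the third is "or increased contamination rates in the lab which is routinely monitored for by our embryologists". For the other class it says: "Non-severe adverse events include adverse effects of antibiotic administration including yeast vaginitis, abdominal pain, diarrhea, nausea and vomiting".

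E5 5.d covers the same ground in different words. On the severe side: "Reportable severe events include development of pelvic infection following embryo transfer, a significant increase in spontaneous miscarriage rates", plus a rise in laboratory contamination. On the non-severe side: "Reportable non-severe adverse events include yeast vaginitis, nausea and vomiting or other adverse reactions from antibiotic prophylaxis". D2 2.e repeats the 5.d split almost word for word.

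Two rules use the word severe. E5 5.e sets the only off-schedule analysis: "Data will be analyzed if a noted increase in severe adverse events is noted". F2 treats the trial as safe to continue given an "absence in trend toward severe adverse maternal, pregnancy or laboratory outcomes in either group".

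Other provisions apply whatever the class. Patients are asked about side effects (5.a). The DSMB reviews adverse events at half enrollment and six-monthly after that (5.b). All events go into the chart and REDCap (5.e). Symptoms that patients report are passed on at once to the PI or the project coordinator (5.f).

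**The concern.** A severity class that drives an action should depend on what happened to the person. Here it depends on the kind of event and its presumed cause. Once a reaction is attributed to the antibiotic, it is non-severe whatever its outcome, and no grade, seriousness criterion or route of escalation is given. A serious event that is neither an antibiotic reaction nor one of the three listed types, such as an admission for a complication of IVF treatment, has no clear class.

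This matters because possible harm from the antibiotic is part of the trial's rationale (B1) and because both partners in male/female couples are dosed (D2 2.d, D3 3.a). The one rule that would bring an analysis forward between scheduled reviews cannot respond, as written, to a serious reaction to the study drug. The continuation rule in F2 leaves open whether it can. The plan also gives two wordings for pelvic infection, the main safety event of interest when prophylaxis is withheld. Nurses and providers know the allocation (D2 2.d), so an ambiguous definition could be applied differently in the two arms.

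**Working it through.** **The plan's own figure.** With a clinical pregnancy rate of 41% in both arms, a 15-point margin, one-sided alpha 0.025 and 80% power (F1):

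n per arm = (1.960 + 0.842)² × 2 × 0.41 × 0.59 / 0.15² = 169 after rounding up; 169 / 0.95 = 178 after rounding up; total 356.

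This matches F1. The point changes no sample-size figure; 178 couples per arm is only the input to the exposure count below.

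**The passages side by side.**

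| Event | 5.c | 5.d and D2 2.e | 5.e trigger | F2 rule |
|---|---|---|---|---|
| Serious antibiotic reaction, woman | Non-severe | Non-severe (catch-all) | Cannot fire | Unclear: F2 does not cite 5.c |
| Serious antibiotic reaction, male partner | Non-severe | Non-severe (catch-all) | Cannot fire | Not maternal, pregnancy or laboratory |
| Other serious event outside the three types | Not listed | Not named; severe list is open-worded | Unclear | Unclear |
| Pelvic infection diagnosed without culture | Not within the definition | Severe: no culture condition | Contradictory | Unclear |

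The first two rows do not depend on whether the severe list is open or closed, because 5.d assigns antibiotic reactions to the other class expressly.

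**Scale.** The rates are assumptions; the documents give none.

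- People dosed over the trial: 178 couples × 2 partners = 356 at most. That this equals the total number of couples is coincidence.
- People dosed by the first scheduled DSMB review: 50% of 356 couples = 178 couples; at 1:1, 89 in the antibiotic arm; 89 × 2 = 178 people at most. At F1's minimum of 7 per week, counted as couples, this point comes at 178 / 7 = about 25 weeks.
- Chance of at least one serious reaction among m people at risk r: 1 − (1 − r)^m. Expected number: m × r.

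| Assumed risk r | Expected, m = 356 | Chance of ≥1, m = 356 | Expected, m = 178 | Chance of ≥1, m = 178 |
|---|---|---|---|---|
| 0.1% | 0.4 | 30% | 0.2 | 16% |
| 0.5% | 1.8 | 83% | 0.9 | 59% |
| 1% | 3.6 | 97% | 1.8 | 83% |

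The m = 178 columns cover the period before any scheduled review, when the off-schedule trigger is the only rule in the plan that prompts an analysis.

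**The case against.** The strongest reply is that nothing goes unseen. A reader might infer that serious reactions escape oversight, but 5.a, 5.b, 5.e and 5.f provide for asking, recording, immediate reporting and scheduled DSMB review of adverse events of any class. That stands. What is missing is the severe label, access to the off-schedule trigger and a clear link to F2.

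Four other strong readings are tempting, and the documents do not support them:

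- *Severe events are a closed list.* 5.c reads that way, but 5.d and D2 2.e introduce their severe events as examples.
- *Serious reactions can never reach F2.* F2 does not refer to 5.c, and a reaction that puts the woman in hospital could be read as a severe maternal outcome. Only the male partner's reaction clearly falls outside.
- *Pelvic infection without a positive culture is excluded.* 5.c asks for a culture and an examination without saying that the culture must be positive, and 5.d and 2.e set no culture condition. The position is contradictory rather than settled.
- *The severe class can show only harms of withholding, so the comparison of arms is lopsided by construction.* Miscarriage is in that class, 5.d expects it to be equal or better without prophylaxis, and B1 describes how antibiotics might harm through the reproductive-tract microbiome. Miscarriage can therefore register harm from the drug.

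The scale figures can also be challenged fairly. The rates are assumed. The counts are ceilings: in same-sex couples only the embryo recipient is dosed, some may not take the drug, and couples with a contraindication are excluded. 5.e needs a noted increase and F2 a trend, so a single reclassified event might change no decision. All of this stands. The figures show how likely the misclassification is to arise, not how often a decision would differ.

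**Conclusion.** The concern holds as a defect of definition and should be corrected. Followed as written, 5.c, 5.d and D2 2.e give a wrong result for a serious antibiotic reaction: it is non-severe by rule and cannot fire the 5.e trigger. This is a stated rule rather than missing detail. Serious events outside the named categories have no clear class. The reach of F2 is uncertain for the woman and does not extend to the male partner. The pelvic-infection wording conflicts between 5.c and the other two sections.

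Its size depends on a serious-reaction risk that the documents do not give, on full uptake by both partners in all 178 couples, and on independence between people. On those assumptions the problem is unlikely but possible at 0.1% (30% over the trial) and close to certain at 1% (97%). The conclusion about the classification needs none of these assumptions. The primary analysis, sample size and treatment are unaffected.

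**What to change.** - In 5.c and 5.d, and where D2 2.e repeats them, define serious events by consequence: death, threat to life, hospital admission or prolongation, lasting disability or equivalent. Apply this to either partner, in both arms and whatever the presumed cause, alongside the three types already listed.
- Limit the non-severe antibiotic category to reactions that do not meet that definition.
- Refer to the same definition in 5.e and F2, so that the off-schedule trigger and the continuation rule use one meaning of severe and cover the male partner.
- Reconcile the pelvic-infection wording of 5.c with 5.d and 2.e, so that one definition applies in both arms.

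The cost is protocol wording, one REDCap field, and a few more events to classify and report.

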We *hypothesize* that subclinical eukaryotic viruses will be associated with negative IVF cycle outcomes.

C3 Rationale for the Selection of Outcome Measures

We expect to define the clinical impact of withholding antibiotic prophylaxis before embryo transfer as measured by markers of a successful IVF cycle. As we hypothesize that withholding prophylaxis will be non-inferior to routine antibiotic administration, these results are expected have a positive clinical impact by decreasing unnecessary broad-spectrum antibiotic exposure and potentially creating a paradigm shift in IVF protocols.

D Study Design

D1 Overview or Design Summary

This will be a prospective randomized controlled non-inferiority trial in which 178 couples will receive the standard of care prophylactic antibiotics (control) and 178 will not receive prophylactic antibiotics (experimental). The primary outcome is clinical pregnancy rate. The expected primary outcome is that withholding prophylactic antibiotics will be non-inferior to antibiotic prophylaxis in terms of clinical pregnancy rate. Secondary outcomes include spontaneous miscarriage rate and embryo development as measured by fertilization rate, blastocyst conversion rate, blastocyst utilization rate, and live birth rate.

D2 Subject Selection and Withdrawal

2.a Inclusion Criteria

The female partner must be aged 18–43 years and going through a fresh IVF cycle. The male partner must be aged 18 at minimum. There is no upper age limit to males.

2.a Exclusion Criteria

Couples will be excluded from enrollment if they have any contraindication to antibiotic treatment (ie: allergy), are not intending to undergo embryo transfer (fertility preservation patients and oocyte donors), require use of extended antibiotic coverage at time of egg retrieval, are already on antibiotics for any reason (e.g., upper respiratory infection), have a recent history of pelvic infection, or are planning on limited insemination (inseminating a limited number of the eggs retrieved).

2.b Ethical Considerations

Participation will be completely voluntary. Patients care will not be impacted in any way by their decision to participate or lack thereof. Incidence of pelvic infection following embryo transfer approaches zero in this low risk population therefore patients are not being placed at any additional undo risk. They may be spared from experiencing potential adverse side effects of the oral antibiotic.

2.c Subject Recruitment Plans and Consent Process

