
Couples going through fresh IVF cycles will be identified and their charts reviewed to assess eligibility for inclusion. Eligible couples will be contacted via phone by a trained study coordinator and offered enrollment. Those who express interest will have a time arranged for both partners to provide written consent in the office. If the patient or couple is unable to find a mutually convenient time to come into the office for consent, both the patient and their partner will be emailed the consent form for review. They will then be consented in full over the phone and given instruction on return of the hard copy of the signed consents. Couples will not be randomized until receipt of the hard copy of their signed consents and review and signature of the research team member providing consent. Couples will only be included in the study during one IVF cycle. Subjects going through their first IVF cycle will also have an introduction to the study during IVF orientation.

2.d Randomization Method and Blinding

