Couples will be randomized after providing written consent. Written consent will be obtained separately for both the male and female partner. In the case of same sex couples, only the female undergoing embryo transfer will be consented. Fifty couples going through their first IVF cycle enrolled in the noninferiority trial will also be offered enrollment in the pilot RCT and subsequently consented for the microbiome and virome profiling exploratory study. After consent, randomization in a 1:1 ratio to prophylactic antibiotics or no antibiotics will be performed in a block-randomized fashion per cycle number via computer random number generator. Couples randomized to the antibiotic group will receive the current standard regimen in our clinic: 1 gram azithromycin oral once for both partners the day controlled ovarian stimulation is initiated with injectable gonadotropins (IVF cycle start). In cases of same-sex couples, only the female undergoing the embryo transfer receives prophylaxis. Couples randomized to the no-antibiotic treatment group will not be prescribed oral antibiotic prophylaxis. Couples who agree to participate will have their charts marked indicating participation in the study. The couples' respective nurses will receive a message that will remain part of the electronic medical record regarding patient treatment group allocation so they can prescribe antibiotics appropriately. Embryologists who assess the embryo outcome measures will be blinded to patient treatment group allocation. The patients and their providers and nurses will not be blinded to treatment group allocation.

2.e Risks and Benefits

Potential problems with our study may be insufficient patient recruitment. The process of IVF is already stressful, time and user intensive and we will have to consent both

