Intention-to-treat and per protocol analyses will be performed. Chi-squared and Fisher's exact tests will be used to compare categorical variables as appropriate. Kolmogorov-Smirnov test will be initially used to assess the distribution pattern of continuous variables. Normally distributed variables will be analyzed via Student's t-test. Non-normally distributed continuous variables will be analyzed with the Mann-Whitney U test. The primary analysis is based on difference in clinical pregnancy rate between the two groups. The sample size estimation for the study is based on this comparison with a non-inferiority approach as described above with an absolute difference of 15% or less to be considered non-inferior. Secondary analyses will include spontaneous miscarriage rate and embryo development. A subsequent interval analysis will assess live birth rate. Pearson's correlation coefficients will be used to quantify the association

between the two groups and embryo development. $P < 0.05$ will be considered statistically significant.

Each microbiota sample will have the taxon indicated as relative abundance. To assess the diversity across an IVF cycle, after log transformation, linear mixed regression will be applied. Wilcoxon rank sum will be used to measure for difference in richness and diversity with clinical outcomes of clinical pregnancy rate, miscarriage rate and embryo outcomes.

IBM® SPSS® statistics version 23 will be used for all analyses.

F5 Missing Outcome Data

All outcome data is required to be tracked by SART and no additional query will be required. We do not anticipate any issues with missing outcome data.

G Data Handling and Record Keeping

G1 Confidentiality and Security

Our practice is required to track patient demographic data and cycle outcome measures to report to the Society for Assisted Reproductive Technology (SART). Data is currently recorded and tracked through Research Electronic Data Capture (REDCap). REDCap is a secure web-based application designed to support data capture for research studies, providing 1) an intuitive interface for validated data entry; 2) audit trails for tracking data manipulation and export procedures; 3) automated export procedures for seamless data downloads to common statistical packages; and 4) procedures for importing data from external sources.¹⁸ Enrolled patients will be exported and tracked in a separate REDCap data set from our existing dataset.

G2 Records Retention

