Study records will be stored and tracked through REDCap as noted in G1. Signed consents will be kept in a locked cabinet in a locked office. Data will be retained until study enrollment and analysis is complete.

H Study Administration

H1 Organization and Participating Centers

Washington University Department of Reproductive Endocrinology and Infertility.

H2 Funding Source and Conflicts of Interest

The PI, [name] is a recipient of funding from NIH 5T32HD055172 as a part of her Masters of Science and Clinical Investigation clinical research track. There are no conflicts of interest to report.

H3 Subject Stipends or Payments

Not applicable.

H4 Study Timetable

See Table 1.

I Publication Plan

We plan on presenting our findings at national meetings including those for American Society for Reproductive Medicine and Society for Reproductive Investigations. We plan to publish our results in journals that have a high impact among reproductive endocrinologists within 6 months of completing our data collection.

J Attachments

J1 Tables

Figure 1: Timetable (months)

	1	2	3	4	5	6	7	8	9	10	11	12	13	14	15	16	17	18	19	
Patient Recruitment	X	X	X	X	X	X	X	X	X	X	X	X	X	X						
Analysis															X	X	X			
Manuscript Composition																	X	X	X	

Table 2. Potential confounders

Patient history	Cycle level factors	Cycle outcome
-----------------	---------------------	---------------

Demographic data: Maternal age, race, ethnicity Medical history: BMI, tobacco use Obstetric history: gravidity, parity Infertility diagnosis Duration of infertility Number of prior IVF cycles Baseline labs: Follicle stimulating hormone or antimullerian hormone level, antral follicle count	Total amount of gonadotropin administered Stimulation protocol Number oocytes collected Number mature oocytes Insemination method (conventional vs. intracyto-plasmic sperm injection [ICSI] vs. partial ICSI) Number oocytes normally fertilized (two pronuclei) Day of embryo transfer Number of embryos transferred Number of embryos frozen	Clinical pregnancy rate Spontaneous miscarriage rate Live birth rate
---	---	--

K References

1. www.sart.org
2. Czernobilsky B. Endometritis and infertility. *Fertil Steril.* 1978;30:119-130.

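### F4 leaves the cycle-number randomisation groups and recorded maternal age out of the primary comparison, which costs some precision but not validity

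*Combined protocol and SAP*

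**What the plan says.** Section D2 2.d (Randomization Method and Blinding) sets the allocation: "randomization in a 1:1 ratio to prophylactic antibiotics or no antibiotics will be performed in a block-randomized fashion per cycle number". The phrase is brief; it is read here as blocks within groups defined by IVF cycle number. The groups themselves are not defined.

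The inclusion criteria in D2 allow a wide age range: "The female partner must be aged 18–43 years and going through a fresh IVF cycle". Section D2 2.c makes the couple the unit, with one cycle each: "Couples will only be included in the study during one IVF cycle". Table 2 in J1 shows that both baseline variables are in hand: "Demographic data: Maternal age, race, ethnicity" and "Duration of infertility Number of prior IVF cycles".

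For the primary endpoint F4 says: "The primary analysis is based on difference in clinical pregnancy rate between the two groups". For categorical data it names chi-squared and Fisher's tests: "exact tests will be used to compare categorical variables as appropriate". It names no stratum, covariate or adjusted model for clinical pregnancy; the only regression model in F4 is for the microbiome samples. F1 gives the design: "with a non-inferiority margin of 15%, 80% power, and using a one sided" alpha of 0.025.

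**The concern.** A factor used to constrain the randomisation is normally carried into the analysis, and a baseline variable that predicts the outcome is normally used if it is already collected. F4 does neither. In a non-inferiority trial the width of the interval matters directly: the claim depends on whether its lower limit clears -15 points. If age or cycle number predicts pregnancy, an unadjusted interval is wider than it needs to be, and power stays at the planned 80% when some more could be had at no cost in couples or data.

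There is one side issue. F3 refers to Table 2 as a list of potential confounders to be addressed, but no section says which items would be used or how. The list mixes baseline items with some that arise after allocation, such as oocyte and embryo counts and day of transfer. It also includes the outcomes themselves.

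**Working it through.** **Inputs from the documents.** Clinical pregnancy rate 41%, margin 15 points, one-sided alpha 0.025, power 80%, drop-out 5%, 178 per arm (all F1); 1:1 allocation (D2 2.d).

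**Input that is assumed.** R², the share of outcome variance explained by the covariates. The documents give no pregnancy rates by age or cycle number.

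**Step 1: reproduce the plan.**
n per arm = (1.960 + 0.842)² × 2 × 0.41 × 0.59 / 0.15² = 168.8, so 169.
169 / 0.95 = 177.9, so 178 per arm and 356 in total. This matches F1.

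**Step 2: precision of the unadjusted analysis.**
SE = √(2 × 0.41 × 0.59 / 169) = 0.0535.
Half-width = 1.96 × 0.0535 = 10.5 points.
Power = Φ(0.15 / 0.0535 − 1.96) = 80.1%.

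**Step 3: precision after adjustment.** Multiply the variance by (1 − R²).

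| R² (assumed) | Half-width (points) | Power |
|---|---|---|
| 0 | 10.5 | 80.1% |
| 0.02 | 10.4 | 80.8% |
| 0.05 | 10.2 | 82.0% |
| 0.10 | 9.9 | 84.0% |

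To help judge these shares: if age alone accounted for them through a linear logistic model, the control rates at ages 30 / 35 / 40 would be 49 / 40 / 32% (R² 0.02), 54 / 40 / 27% (0.05) and 59 / 39 / 21% (0.10).

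**Step 4: cycle-number groups alone.** With assumed group sizes of 60 / 25 / 15% and assumed rates of 41 / 41 / 41, 46 / 36 / 30 or 50 / 32 / 20%, the gain is about 0 to 2 points of power.

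**Step 5: simulation of a standardised logistic estimator.** The set-up was 338 couples, permuted blocks of 4 within three cycle-number groups, age normal (mean 35, SD 4.5) truncated to 18–43, and a control rate of 41%. Group sizes, block size and age distribution are assumptions. There were 20,000 trials for power and 30,000 for error.

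- Power, unadjusted to adjusted: 80.0 to 80.1% (age R² 0), 79.7 to 80.6% (0.02), 79.9 to 82.0% (0.05), 80.1 to 84.4% (0.10).
- Age truly flat to 35 and then falling, but modelled as linear: 79.8 to 81.4% (0.05) and 80.0 to 83.2% (0.10).
- False non-inferiority at a true loss of 15 points, over 12 scenarios: 2.2–2.6% unadjusted and 2.4–2.6% adjusted. Neither departs materially from 2.5%.

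A separate simulation with a linear adjusted model and a mild age gradient gave power of 80.4% unadjusted and 81.4% adjusted, with both analyses essentially unbiased.

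**The case against.** The strongest reply is that nothing here is wrong. An unadjusted risk difference is a legitimate primary analysis, it matches the basis of the sample size in F1, and its error rate is correct. The gain rests wholly on an assumed R². At 2–5% it is about 1 to 2 points of power and 0.1 to 0.3 points of half-width, and an R² of 10% implies a steep age gradient. All of this stands. It limits the point to an improvement, and it does not remove the case for one that needs no data and no couples.

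It is also fair to say that the missing confidence interval in F4 is a separate gap. It adds no weight here, although the same sentence in F4 can close it.

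A further fair objection is that age needs a definition. Section D3 3.a mentions gestational carriers and same-sex couples, so the oocyte source and the embryo recipient may be different women.

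A reader might infer two stronger points. The first is that ignoring the randomisation groups biases the result or makes 356 too few. The calculations show neither. The second is that the plan will adjust for the post-allocation items in Table 2 and so remove part of any treatment effect. F4 plans no such model, F3's sentence is mainly about data being available, and a list that contains clinical pregnancy itself cannot literally be a covariate list for it. Followed as written, the plan gives no wrong result on this score; what remains is a clarification.

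**Conclusion.** The point holds as a matter of precision only. F4 leaves out the factor used in randomisation and a recorded baseline variable. The unadjusted difference is valid and the sample size does not change. Adjustment would raise power from 80.1% to between 80.8% and 84.0%, and cut the half-width from 10.5 to between 10.4 and 9.9 points, if the covariates explain 2–10% of outcome variance. If they explain none, nothing material is gained or lost. The result rests on that assumed range and on reading the blocking as stratification by IVF cycle number. The change is worth making because it is nearly free, not because the present analysis is in error.

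**What to change.** In F4:

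- Make the primary estimate a risk difference in clinical pregnancy (no antibiotics minus antibiotics), adjusted for the cycle-number randomisation groups and baseline female age. Logistic regression standardised over the analysed couples, with robust variance, is one suitable method.
- Report a two-sided 95% confidence interval, which matches the one-sided 0.025 in F1, and claim non-inferiority if its lower limit is above -15 points.
- State whose age is used when the oocyte source and the embryo recipient differ.
- Define the cycle-number groups, and fix a rule for merging sparse ones before outcome data are seen.
- Limit covariates in any comparison of arms to baseline variables, and relabel Table 2 as baseline covariates, post-randomisation descriptors and outcomes.
- Keep the unadjusted difference with its 95% interval as a sensitivity analysis.

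The cost is a few sentences of text and a little more analysis work. F4 names SPSS 23 for all analyses; confirm that it can produce the standardised interval, or name a supplementary package. No new data are needed and 356 is unchanged.

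### F4 carries the 15-point margin forward but not the test against it: no confidence limit is named, and its criterion, read literally, applies to the observed difference

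*Combined protocol and SAP*

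**What the plan says.** F1 (Sample Size Determination and Power) sets 178 couples per arm from a 41% baseline clinical pregnancy rate, a "non-inferiority margin of 15%, 80% power, and using a one sided" alpha of 0.025, and 5% dropout. The hypothesis in C1 also puts non-inferiority as an absolute difference of at most 15%.

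F4 (Statistical Methods) bears on the primary decision in four places:

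- Target: "The primary analysis is based on difference in clinical pregnancy rate between the two groups".
- Link to the design: "The sample size estimation for the study is based on this comparison with a non-inferiority approach as described above", and the same sentence continues "with an absolute difference of 15% or less to be considered non-inferior".
- Tests for binary outcomes: chi-squared and Fisher's "exact tests will be used to compare categorical variables as appropriate".
- Threshold: P<0.05 counts as significant, with no side given.

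Neither F1, F4 nor C1 states a confidence limit or a test against the margin. F4 uses the word interval once, in "A subsequent interval analysis will assess live birth rate". That concerns a different outcome and reads as a later analysis, not a confidence interval.

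**The concern.** A non-inferiority conclusion needs a rule that allows for sampling error, usually that the confidence limit on the unfavourable side lies within the margin. F1 assumes such a rule. F4 repeats the margin but does not say what is compared with it: the true difference, the observed difference or a confidence limit.

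An analyst who follows F4's words alone has two things to work with. One is a criterion that reads as a rule for the point estimate. The other is a pair of tests whose null hypothesis is no difference, and a non-significant result from either is not evidence of non-inferiority. Neither route gives the 2.5% error rate that F1 paid for in sample size. What is at stake is the trial's one primary conclusion: whether withholding prophylaxis can be called non-inferior.

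**Working it through.** **Inputs.** Control rate 41%, margin 15 points, one-sided alpha 0.025, power 80%, dropout 5%, 178 per arm (all F1); 1:1 allocation (D2 2.d). Assumption: 41% in both arms for power, since the plan gives no separate rate for the no-antibiotic arm. Evaluable number: 178 × 0.95 = 169.1, so 169 per arm.

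**1. Reproduce F1.** n = (1.960 + 0.8416)² × 2 × 0.41 × 0.59 / 0.15² = 168.8, so 169 per arm. 169 / 0.95 = 177.9, so 178 per arm and 356 in total. This matches F1. The same formula at one-sided 0.05 gives 132.9, so 133 per arm (140 with dropout), which does not match. F1's N therefore belongs to a one-sided 0.025 test against the margin.

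**2. False non-inferiority at the margin.** True rates 41% and 26%, a single final look, all pairs of binomial counts enumerated:

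| Rule | 169 per arm | 178 per arm |
|---|---|---|
| Lower two-sided 95% limit above -15 points, Wald | 2.5% | 2.5% |
| Same, Newcombe | 2.6% | 2.6% |
| Non-significant chi-squared taken as non-inferior | 16.3% | 14.5% |
| Observed loss of 15 points or less | 50.6% | 49.0% |

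Hand checks at 169 per arm:

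- *Observed-difference rule.* The estimate is centred on -15 points when the true loss is 15, so about half of all trials pass.
- *Chi-squared rule.* The pooled rate is 0.335, with standard error √(2 × 0.335 × 0.665 / 169) = 0.0513, so losses below 1.96 × 0.0513 = 0.101 are non-significant. The standard error of the difference is √((0.41 × 0.59 + 0.26 × 0.74) / 169) = 0.0507. Then (0.101 - 0.150) / 0.0507 is about -0.97, a probability of about 16.5%, close to the enumerated 16.3%.

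**3. Single results at 169 per arm.**

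- 69 against 55 pregnancies: rates 40.8% and 32.5%, difference -8.3 points. Standard error √((0.408 × 0.592 + 0.325 × 0.675) / 169) = 0.0522, so the Wald 95% interval is -8.3 ± 10.2, or -18.5 to +2.0 (Newcombe -18.3 to +2.0). Chi-squared P = 0.11. The limit rule fails; the observed-difference and non-significance rules both pass.
- 41% observed against 27%: a 14-point loss with a 95% interval of about 4.0 to 24.0 points. The literal criterion passes, although the interval excludes no loss at all.

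**4. Where the rules part.** With 41% observed in the control arm and 169 per arm, the largest observed loss that satisfies the 95% limit is about 4.6 points (Wald). Losses from there to about 10.2 points are non-significant yet fail the limit. The literal criterion passes everything up to 15.

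**5. Power under a stated limit rule.** No true difference: Wald 79.9% at 169 and 82.1% at 178 per arm; Newcombe 80.9% and 82.5%.

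**The case against.** The strongest reply is that the rule is there by reference. F1 gives margin, side and alpha; F4 names the difference as the primary analysis, points back to the non-inferiority approach and repeats the 15%. Much of this stands. The margin is carried forward, and a margin test is the best-supported reading. But the subject of F4's sentence is the sample size estimation, and the sentence that would link a confidence limit to the margin appears nowhere.

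Three stronger readings are tempting, and the documents do not support them.

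- *The plan tells the analyst to treat a non-significant chi-squared as non-inferiority.* It does not. Those tests are listed for categorical variables in general. The 16% figure shows what F4 fails to exclude. The observed-difference rule has more literal support, but it too is a reading; in C1's hypothesis the same 15% is naturally about the true difference.
- *F4's P<0.05 contradicts F1 and doubles the error to 5%.* This needs P<0.05 to be one-sided. It closes a paragraph of tests that are ordinarily two-sided, and two-sided 0.05 corresponds to a 95% interval, each limit of which is a one-sided 0.025 test. F1's N also fits only 0.025. The fair statement is that the side is not given and the two sections agree if it is two-sided.
- *A particular interval method is required.* Wald and Newcombe rarely disagree. They do at 69 against 61 of 169 (lower limit -15.1 by Wald, -14.9 by Newcombe). That is a reason to name one in advance, not to insist on either.

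**Conclusion.** The concern holds as a gap in the primary decision rule. F4 states the margin without the test against it. As written, F4 does not secure F1's 2.5% error rate: followed literally, its criterion gives about 51% at a true 15-point loss, and a non-significant chi-squared taken as non-inferiority gives about 16%. These figures assume 41% against 26%, 169 evaluable couples per arm and a single final analysis; the interim looks in F2 ("Interim analysis will be performed according to the Haybittle-Peto approach at 50% enrollment and 75% enrollment") are ignored. At 178 per arm the figures are 49.0% and 14.5%.

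The sample size is not in error, and the sponsor may well intend the 95% limit rule. The case for correction is that the rule for the sole primary conclusion has to be inferred, in a trial where patients, providers and nurses know the allocation and looks at the data are planned during enrolment.

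**What to change.** State in F4:

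- The primary analysis is the difference in clinical pregnancy proportion, no antibiotics minus antibiotics, with a two-sided 95% confidence interval by one pre-named method. Wald and Newcombe are both acceptable; give the formula, or confirm that the software named in F4 produces the interval.
- Non-inferiority is declared only if the lower limit is above -15 percentage points, equivalent to one-sided 0.025 as in F1.
- Chi-squared, Fisher's exact and P<0.05, stated as two-sided, apply to the other comparisons.

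**Cost.** Wording only. N stays 356, and power at no true difference is about 80-81% at 169 per arm. The price is that observed losses of roughly 5 to 15 points can no longer be called non-inferior. If Newcombe is chosen, its error at the margin is 2.6%, slightly above nominal. This wording does not settle how the F2 looks affect the final test.

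**Separate matter, adding no weight to the above.** F4 plans both intention-to-treat and per-protocol analyses without saying which decides. D2 2.f leaves couples without retrieval or transfer out of the analysis, and D2 2.h does the same for withdrawals. Reconcile these exclusions with the intention-to-treat analysis and name the deciding analysis set.
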